6.2.3 Rescue medication

The following circumstances warrant discontinuation of study treatment (during the treatment period) and the implementation of rescue medication by the investigator (Commencement of rescue medication may occur after the start of study drug and up to Day 43):

Early Treatment Failure (ETF)

- Development of danger signs or severe malaria on Day 2, Day 3, Day 4 in the presence of parasitemia.
- Parasitemia on Day 3 higher than Day 1 count irrespective of axillary temperature.
- Parasitemia on Day 4 with axillary temperature $\geq 37.5^\circ$.
- Parasitemia on Day 4 equals to or more than 25% of count on Day 1.

Late Clinical Failure (LCF)

- Development of danger signs or severe malaria on any day from Day 5 to Day 43 in the presence of parasitemia without previously meeting any of the criteria of Early Treatment Failure.
- Presence of parasitemia and axillary temperature $\geq 37.5^\circ$ on any day from Day 5 to Day 43 without previously meeting any of the criteria of Early Treatment Failure.

Late Parasitological Failure (LPF)

- Presence of parasitemia on any day from Day 8 to Day 43 and axillary temperature $< 37.5^\circ$ without previously meeting any of the criteria of Early Treatment Failure or Late Clinical Failure.

Rescue treatment involves therapy with an effective antimalarial available locally as per local medical practice or National Treatment Guidelines. Administration may be oral or parenteral depending on the subject's clinical condition. Rescue treatment will not be considered study medication. The exact rescue regimen and route of administration must be recorded on the appropriate CRF.

Patients will be monitored, either in clinic, or via home visits for the duration of treatment to ensure adherence to the rescue medication therapy. These patients will not discontinue the study (i.e., all the examinations as per the assessment schedule and all CRF for this patient will need to be completed), and they will not be replaced (unless the PK data cannot be properly analyzed due to treatment schedule discontinuation).

6.3 Subject numbering, treatment assignment, randomization

6.3.1 Subject numbering

Each subject is uniquely identified in the study by a Subject Number (Subject No.), that is assigned when the subject enters screening and it is retained as the primary identifier for the subject throughout his/her entire participation in the trial. The Subject No. consists of the Center Number (Center No.) (as assigned by Novartis to the investigative site) with a sequential subject number suffixed to it, so that each subject is numbered uniquely across the entire database. Once assigned to a subject, the Subject Number will not be reused.

Upon their parent/legal guardian signing the informed consent form, the subject is assigned to the next sequential Subject No. available. The investigator or his/her staff will then contact the Interactive Response Technology (IRT) and provide the requested identifying information for the subject to register them into the IRT. The site must select the CRF book with a matching Subject Number from the electronic data capture (EDC) system to enter data.

6.3.2 Treatment assignment, randomization

No randomization will be performed in this study. All eligible subjects will be assigned to one of the treatment packs via Interactive Response Technology (IRT). The investigator or their delegate will contact the IRT after confirming that the subject fulfills all the inclusion/exclusion criteria. The IRT will assign a unique medication number for the package of study treatment and the dose level to be dispensed to the patient.

If the patient fails to be treated for any reason, the IRT must be notified within 2 days that the patient was not treated. The reason for not being treated will be entered on the appropriate disposition CRF.

6.4 Treatment blinding

This study is open label and treatment as well as the dose level will be open to the subjects' parents/legal guardian, investigator staff, persons performing the assessments, and the CTT.

6.5 Dose escalation and dose modification

6.5.1 Dose escalation guidelines

6.5.1.1 Starting dose

The starting dose in Cohort 1 in this trial is artemether:lumefantrine 5 mg:60 mg, i.e., 2 tablets bid for 3 days.

6.5.1.2 Provisional dose levels

[Table 6-3](#) describes the starting dose and the dose levels that may be evaluated during this trial.

Table 6-3 Provisional dose levels

| Dose level | Proposed dose* | Number of tablets per dose** |
|------------|---|------------------------------|
| 1 | 2.5 mg:30 mg | 1 |
| 2 | 5 mg:60 mg (starting dose in Cohort 1) | 2 |
| 3 | 7.5 mg:90 mg | 3 |
| 4 | 10 mg :120 mg | 4 |

*administered bid over 3 days.

**Dose level number 1 represent treatment regimen if a dose reduction is required from the starting dose level number 2 (used in Cohort 1) while Dose level numbers 3 and 4 represent treatment regimens if a dose increase is required. No dose reduction below dose level number 1 nor dose increase above dose level number 4 is permitted for this study.

Dose modification in a particular subject is not permitted. However, each cohort will be divided into sequential groups (see [Figure 3-2](#) and [Table 6-3](#)). A pharmacokinetic exposure check (together with a review of efficacy and safety data as available) will be performed as described in [Section 3](#) and [Section 4.2](#). Based on the outcome of these checks, the dose may be adjusted between dose levels 1-4 in further patients recruited, following a pattern specific to each cohort. For more details, see [Section 6.1.3](#).

6.5.2 Dose modifications

Dose level modification may not occur in an individual patient's 6-dose regimen, but the dose level may be adjusted between patients after each PK exposure check (See [Section 6.5.1.2](#)).

In addition, a replacement dose may be given to a patient in case of vomiting of a dose within 1 hour of administration (see [Section 6.7.2](#)). In case this repeat dose is vomited within 1 hour of intake, rescue treatment should be immediately provided.

6.5.3 Follow-up for toxicities

See [Appendix 2 - Section 16.2](#)

6.6 Additional treatment guidance

6.6.1 Treatment compliance

A limited number of qualified individuals, will be designated as appropriate by the investigator in order that two of these people ensure compliance by direct observation of both preparation

and administration of all doses of study medication for each patient. The exact dosages administered will be recorded on the Dosage Administration Record CRF, along with any comments about whether the patient swallowed all or only part of the medication, whether and when vomiting occurred, and whether replacement medication had to be initiated.

Pharmacokinetic parameters (measures of treatment exposure) will be determined in all subjects, as detailed in [Section 12.5.3](#).

Records of study medication used and exact doses administered will be kept during the study. Drug accountability will be noted by the field monitor during site visits and at the completion of the study.

6.6.2 Recommended treatment of adverse events

Medication used to treat adverse events (AEs) must be recorded on the appropriate CRF (see [Section 6.2.1](#)).

6.6.3 Emergency breaking of assigned treatment code

Not applicable.

6.7 Preparation and dispensation

Each study site will be supplied with study drug in packaging as described in [Table 6-1](#).

A unique medication number is printed on the study medication label.

Investigator staff will identify the study medication kits to dispense to the subject by contacting the IRT and obtaining the medication number(s) as well as the appropriate dose level.

The study medication has a 2-part label (base plus tear-off label). Immediately before preparing and dispensing the medication kit to the subject, site personnel will detach the outer part of the label from the packaging and affix it to the source document.

If a patient vomits study drug within 1 hour of intake, a replacement dose will be given to the patient and the investigator or designee will notify IRT.

6.7.1 Handling of study treatment and additional treatment

6.7.1.1 Handling of study treatment

Study treatment must be received by a designated person at the study site, handled and stored safely and properly and kept in a secured location to which only the investigator and designated site personnel have access. Upon receipt, study treatment must be stored according to the instructions specified on the labels and in the Investigator's Brochure. Clinical supplies are to be dispensed only in accordance with the protocol. Technical complaints are to be reported to the respective Novartis/ CO Quality Assurance.

Medication labels will be in the appropriate local language and comply with the legal requirements of each country. They will include storage conditions for the study treatment but no information about the subject except for the medication number.

The investigator must maintain an accurate record of the shipment and dispensing of study treatment in a drug accountability log. Monitoring of drug accountability will be performed by monitors during site visits or remotely and at the completion of the trial.

At the conclusion of the study, and as appropriate during the course of the study, the investigator will return all unused study treatment, packaging, drug labels, and a copy of the completed drug accountability log to the Novartis monitor or to the Novartis address provided in the investigator folder at each site.

6.7.1.2 Handling of additional treatment

Rescue medication will be handled as per [Section 6.2.3](#).

6.7.2 Instruction for prescribing and taking study treatment

Two qualified individuals (from a limited number of people designated by the investigator for this task) will directly observe preparation and administration of all doses of study medication. They should promote compliance by ensuring that the patient take the study drug exactly as prescribed and by stating to the patient's legal guardian that compliance is necessary for the patient's safety and the validity of the study.

The study drug (dispersible tablets) should be administered as follows: the appropriate number of dispersible tablets composing 1 dose should be completely dispersed in a small amount of clean water (approximately 3 mL per dose) using a syringe for oral use and its content should be shaken gently and administered immediately to the subject (i.e., within 10 min). The syringe should then be rinsed with an additional small amount of clean water (approximately 3 mL) and given immediately to the subject (further details can be found in the Pharmacist instruction manual). The dose should be preceded and/or followed as much as possible by food/drinks rich in fat such as breast milk, or formula milk, in order to enhance absorption as well as to avoid dehydration.

In the event of vomiting of a dose within 1 hour of administration a repeat dose should be administered. In case this repeat dose is vomited within 1 hour of intake, rescue treatment should be immediately initiated and the infant discontinued from the study medication. The exact rescue regimen and route of administration (see [Section 6.2.3](#)) is to be recorded on the appropriate CRF.

For Dose 2 (at Hour 8), the administration time window should not be greater than \pm 1 hour to achieve effective plasma level as soon as possible after start of treatment. For the following doses at Hours 24, 36, 48 and 60 (twice daily), the time window should not be greater than \pm 2 hours. During the 3-day treatment period, study medication will be given under hospital supervision.

All kits of study treatment assigned by the IRT will be recorded in the IRT system.

7 Informed consent procedures

Eligible subjects may only be included in the study after IRB/IEC-approved informed consent (witnessed, where required by law or regulation) has been provided by their legally acceptable representative (LAR), i.e. parent or legal guardian.

Informed consent must be obtained before conducting any study-specific procedures (e.g. all of the procedures described in the protocol). The process of obtaining informed consent must be documented in the subject source documents.

Novartis will provide to investigators in a separate document a proposed informed consent form that complies with the ICH GCP guidelines and regulatory requirements and is considered appropriate for this study. Any changes to the proposed consent form suggested by the investigator must be agreed by Novartis before submission to the IRB/IEC.

Information about common side effects already known about the investigational drug can be found in the Investigator's Brochure (IB). This information will be included in the informed consent and should be discussed with the subject's LAR during the study as needed. Any new information regarding the safety profile of the investigational drug that is identified between IB updates will be communicated as appropriate, for example, via an investigator notification or an aggregate safety finding. New information might require an update to the informed consent and then must be discussed with the subject.

A copy of the approved version of all consent forms must be provided to Novartis/sponsor after IRB/IEC approval.

8 Visit schedule and assessments

The assessment schedule ([Table 8-1](#)) lists all of the assessments when they are performed. All data obtained from these assessments must be supported in the subject's source documentation.

Table 8-1 Schedule of assessments

| Day* | 1 | | | 2 | | 3 | | 4 | 5 | 8 | 15 | 29 | 43 | Age 365 days |
|--|---|----|----|-----|-----|-----|-----|-----|-----|------|-----|-----|-----|--------------|
| Hours | -24 to <0h | 0h | 8h | 24h | 36h | 48h | 60h | 72h | 96h | 168h | | | | |
| Informed Consent | X | | | | | | | | | | | | | |
| Inclusion/Exclusion criteria | X | | | | | | | | | | | | | |
| Demography | X | | | | | | | | | | | | | |
| Medical history | X | | | | | | | | | | | | | |
| Prior or concomitant medication | X | X | X | X | X | X | X | X | X | X | X | X | X | |
| Malaria Blood Film | X | | X | X | X | X | X | X | X | X | X | X | X | |
| IRT contact | X | X | X | X | X | X | X | X | X | X | X | X | X | X |
| Drug administration | | X | X | X | X | X | X | | | | | | | |
| Meal Record | | X | X | X | X | X | X | | | | | | | |
| Weight/Height (length) | X | | | X | | X | | X | X | X | X | X | X | X |
| Vital signs | X | X | X | X | X | X | X | X | X | X | X | X | X | |
| Head circumference | X | | | | | | | | | | | | | X |
| Physical Exam | S | S | S | S | S | S | S | S | S | S | S | S | S | S |
| Blood chemistry/ Hematology | X | | | X | | | X | | | X | X | | | X |
| Sample for PCR | X | | | | | | | | | (X) | (X) | (X) | (X) | |
| Neuro-devt. Safety FU | | | | | | | X | | | | | | | X |
| PK sample | According to separate PK sampling scheme (See Section 16.3, Appendix 3) | | | | | | | | | | | | | |
| Adverse events | ↔ | | | | | | | | | | | | | |
| Serious Adverse events | ↔ | | | | | | | | | | | | | |

*To conform with Novartis internal standards, Day 1 is considered baseline (as opposed to Day 0 following WHO terminology); as visits should be scheduled in full 24-hour periods, days after Day 1 visit, say Day 7 visit should occur 7 full days after Day 1 visit, i.e. often on the 8th day

Subjects should be seen for all visits/assessments as outlined in the assessment schedule (Table 8-1) or as close to the designated day/time as possible. Missed or rescheduled visits should not lead to study discontinuation. Subjects who prematurely discontinue the study for any reason should be scheduled for a visit as soon as possible, at which time all of the assessments listed for the final visit of the core follow-up period (Day 43) will be performed. At this final visit, all dispensed investigational product should be reconciled, and the adverse events and concomitant medications recorded on the CRF.

8.1 Screening

The investigator or their delegate will contact the IRT when a patient enters screening. It is permissible to re-screen a subject if they fail the initial screening; however, each case must be discussed and agreed with the Sponsor on a case-by-case basis.

They will contact again IRT after confirming that the patient fulfills all the inclusion/exclusion criteria, to get a unique medication number for the package of study treatment and the dose level to be dispensed to the patient.

8.1.1 Information to be collected on screening failures

Subjects whose legal guardian sign an informed consent form and who are subsequently found to be ineligible will be considered a screen failure. The reason for screen failure should be entered on the applicable CRF. The demographic information, informed consent, and Inclusion/Exclusion pages must also be completed for screen failure subjects. No other data will be entered into the clinical database for subjects who are screen failures, unless the subject experienced a serious adverse event during the screening phase (see SAE section for reporting details).

Subjects whose legal guardian sign an informed consent and who are considered eligible but fail to be started on study treatment for any reason will be considered an early terminator. The reason for early termination should be captured on the appropriate disposition CRF.

8.2 Subject demographics/other baseline characteristics

Country-specific regulations should be considered for the collection of demographic and baseline characteristics in alignment with the CRF.

Patient demographic and baseline characteristic data to be collected on all patients include: age (in days), sex, race, ethnicity, birth weight, current body weight, height, temperature, and malaria blood smears/parasite counts. Relevant medical history/current medical condition data and concomitant medication significant non-drug therapies prior to start of study drug consist in data up to the start of study drug. Where possible, diagnoses and not symptoms will be recorded.

In addition, all medications and significant non-drug therapies administered to a mother (or the person) providing breastmilk to a patient before the patient enters the study and starts treatment with study drug must be listed on the specific Concomitant medications/Significant non-drug therapies prior to start of study drug (e)CRF.

8.3 Efficacy

Efficacy assessments will consist of parasitemia determinations in peripheral blood and body temperature measurement, as well as signs and symptoms of early treatment failure.

Methods of parasitemia assessment

- Giemsa stained thick (and thin) films will be examined. Thin films are only required in the case of confirmation of species other than *P. falciparum*.
- Examination will be done using a light binocular microscope fitted with an oil immersion lens.
- Thick film screening examination (prior to patient inclusion into the trial):
- At least 200 thick film fields are examined. If there is no *P. falciparum*, the slide is declared negative, and the patient is not suitable for inclusion.

- If asexual forms of Plasmodia are found, a total of 200 thick film fields are to be screened for *Plasmodium* species other than *P. falciparum*.
- When it has been ascertained that *P. falciparum* is present, a count is made of the asexual forms against leukocytes, using a tally counter. Counting needs to be done based on at least 200 leukocytes according to the WHO standards. If less than 100 parasites, counting will be extended to 500 leukocytes.
- The parasite density will be calculated according to the following formula:

$$\text{Number of } Plasmodium \text{ parasites} \times \text{actual leukocytes (WBC*)}$$

$$\text{Parasite density per } \mu\text{l} = \frac{\text{Number of leukocytes (WBC) counted (200)}}{\text{Number of leukocytes (WBC) counted (200)}}$$

* WBC at screening or the latest available one

- Blood examination during the 43-day core trial period:
- A total of 200 thick films **fields** are examined (tally counter) before a slide can be pronounced negative.
- If asexual forms of *P. falciparum* are present, a parasite count is required
- If *Plasmodium* species other than *P. falciparum* are found, note species
- If *P. falciparum* gametocytes are seen, perform a gametocyte count against 1000 leukocytes

The count should be made for each species and for the *P. falciparum* gametocytes. Thick (and thin blood) films will be taken at each visit and evaluated by standard techniques (Giemsa stain). This will be the definitive test for a positive *P. falciparum* infection. The parasite counts can also be quantified in % (per 1000) of red cells in the thin film.

For quality control purposes, all slides will be double read by two independent microscopists (as per each site's laboratory standard procedure and quality control measures).

In addition, central reading of all slides will be performed at a central reference laboratory. The results of the local reading will be entered in the (e)CRF and results of the central readings will be sent electronically by the central laboratory to Novartis (or a designated CRO). Results from the central reading will be used for the derivation of primary and secondary efficacy endpoints.

Blood samples for molecular diagnostic purposes

Blood will be sampled for parasite genotyping (PCR) as indicated in the assessment schedule ([Table 8-1](#)). At screening, a blood sample will be collected in all patients fulfilling eligibility criteria for inclusion in the study. A second blood sample will be analyzed only in patients showing treatment failure. This will allow to distinguish between recrudescence and a new infection. Sample analysis will be performed at a pre-selected reference laboratory.

Microscopic species identification (parasitemia) will be confirmed and determined with PCR-based methods on blood retained from samples collected at the time of treatment failure.

All parasite samples at baseline will also be screened for specific genes/single-nucleotide polymorphisms (SNPs) that are known as markers for *P. falciparum* resistance.

During the analysis process no human DNA will be amplified or analyzed by any means.

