5.1 Inclusion criteria

Subjects eligible for inclusion in this study must meet **all** of the following criteria:

1. Male or female neonates / infants
2. Body weight <5 kg but ≥ 2 kg
3. In Cohort 1, infants aged >28 days; in Cohort 2, neonates aged 1 to ≤ 28 days (3 subgroups: 15-28 days; 8-14 days; 1-7 days)
4. Microscopically confirmed diagnosis of *P. falciparum* malaria (or mixed infections)
 - in Cohort 1: of ≥ 500 and $<100,000$ parasites/ μ L asexual *P. falciparum* parasitemia
 - in Cohort 2: of ≥ 100 and $<100,000$ parasites/ μ L asexual *P. falciparum* parasitemia
 - either congenital or neonatal
 - either symptomatic or asymptomatic
5. Parental/legal guardian informed consent obtained and signed prior to any study related procedure. If the parent/legal guardian is unable to read or write, then a witnessed consent according to local ethical standards is permitted (formally documented and witnessed, via an independent trusted witness)
6. The parent/legal guardian is able to understand and comply with protocol requirements, instructions and protocol-stated restrictions for their child and is likely to complete the study as planned

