2.1.1.1 Clearance and treatment failure definitions

Fever Clearance time (FCT), defined as time from the first dose until the first time the axillary body temperature decreased below and remained below 37.5°C axillary or 38.0°C oral/tympanic/rectal for at least a further 24 hours. Note: 38.0°C is the temperature threshold for fever using oral/tympanic/rectal, which will be also used in the treatment failure definition.

Parasite clearance time (PCT), defined as time from the first dose until the first total and continued disappearance of asexual parasite forms which remained at least a further 48 hours.

Early Treatment Failure (ETF)

- Development of danger signs or severe malaria on Day 2, Day 3, Day 4 in the presence of parasitaemia.

- Parasitaemia on Day 3 higher than Day 1 count irrespective of axillary temperature.
- Parasitaemia on Day 4 with axillary temperature $\geq 37.5^\circ$.
- Parasitaemia on Day 4 equals to or more than 25% of count on Day 1.

Late Clinical Failure (LCF)

- Development of danger signs or severe malaria on any day from Day 5 to Day 43 in the presence of parasitaemia without previously meeting any of the criteria of Early Treatment Failure.
- Presence of parasitaemia and axillary temperature $\geq 37.5^\circ$ on any day from Day 5 to Day 43 without previously meeting any of the criteria of Early Treatment Failure.

Late Parasitological Failure (LPF)

- Presence of parasitaemia on any day from Day 8 to Day 43 and axillary temperature $<37.5^\circ$ without previously meeting any of the criteria of Early Treatment Failure or Late Clinical Failure.

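### The only parasite-density formula prints 200 as the leukocytes counted although low counts must run to 500; applied as printed, it overstates density 2.5-fold around both lower entry limits

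*Protocol*

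**What the plan says.** Protocol 8.3 gives the counting rule under the heading "Thick film screening examination (prior to patient inclusion into the trial". The rule has two parts: "Counting needs to be done based on at least 200 leukocytes according to the WHO standards", and then "If less than 100 parasites, counting will be extended to 500 leukocytes". The density formula follows directly. It multiplies the parasite count by the patient's leukocyte count, footnoted as "WBC at screening or the latest available one", and divides by "Number of leukocytes (WBC) counted (200". Neither document gives another density formula.

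For films during the 43-day core period, the same section requires a count when asexual *P. falciparum* forms are seen. It gives no leukocyte number and no formula for that count. All slides are also read centrally, and the central result feeds the efficacy endpoints. The central counting rule is not stated.

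Density is used in three places:

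- **Entry (Protocol 5.1):** at least 500/µL in Cohort 1, at least 100/µL in Cohort 2, and below 100,000/µL in both.
- **Per-protocol set (SAP 5.8):** the same limits are exclusion criteria INCL04A and INCL04B.
- **Early treatment failure (ETF):** two of the four criteria compare counts. One is "Parasitemia on Day 4 equals to or more than 25% of count on Day 1" (Protocol 6.2.3; SAP 2.1.1.1 has "Parasitaemia on Day 4 equals to or more than 25% of count on Day 1"). The other is a Day 3 count above the Day 1 count.

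**The concern.** The extension rule and the bracketed number disagree on every slide that is extended. Two readers who each follow the protocol can report densities that differ by a fixed factor for the same slide. The disagreement falls where density decides something, because slides near the lower entry limits are always extended.

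At stake is who enters and who stays in the per-protocol set. That set carries PCR-corrected ACPR (SAP 2.7.2.1) and the sensitivity analysis of artemether Cmax (SAP 2.5.4). With about 22 patients per cohort, one misclassified patient is 1/22, or about 4.5 percentage points. The rationale for Amendment 1 says that Cohort 2.2 was still recruiting, so screening slides were still to come.

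**Working it through.** The plan states no worked density, so there is no figure to reproduce. The inputs are the 200 and 500 leukocyte rules, the 100-parasite switch and the printed formula (Protocol 8.3), and the limits in 5.1 and 6.2.3. No WBC value is given; I assume 5,000 to 20,000/µL. I take the switch to mean fewer than 100 parasites after 200 leukocytes.

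**1. Size of the discrepancy.** For *p* parasites seen over 500 leukocytes:

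- divided by the number counted: p × WBC / 500
- divided by the printed number: p × WBC / 200
- ratio: 500/200 = 2.5, whatever *p* and WBC are.

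**2. Which slides are extended.** Those with density below 100 × WBC / 200 = WBC/2.

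| Assumed WBC (/µL) | Extended below (/µL) |
|---|---|
| 5,000 | 2,500 |
| 8,000 | 4,000 |
| 10,000 | 5,000 |
| 15,000 | 7,500 |
| 20,000 | 10,000 |

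The 500/µL limit is in the extended range whenever WBC exceeds 1,000/µL, and the 100/µL limit whenever it exceeds 200/µL. The 100,000/µL limit corresponds to 100,000 × 200 / WBC = 4,000 parasites (WBC 5,000) down to 1,000 (WBC 20,000), so it is never affected.

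**3. Effect at the lower limits if 200 is used literally.**

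- Cohort 1: 500/2.5 = 200, so true densities of 200 to 499/µL pass. At WBC 10,000, 10 parasites per 500 leukocytes is 200/µL but reads 10 × 10,000/200 = 500/µL.
- Cohort 2: 100/2.5 = 40, so true densities of 40 to 99/µL pass. At WBC 10,000, 2 parasites per 500 is 40/µL but reads 100/µL. At WBC 20,000, a single parasite per 500 (40/µL) reads 100/µL.

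**4. Early treatment failure.** Let *r* be the true Day 4/Day 1 ratio, with the same WBC on both days and a literal 200. Three cases follow, depending on what the core-period text is taken to mean.

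- *Same rule on all films, Day 1 counted on 200, Day 4 extended.* The ratio reads 2.5r, so 25% is reached at r = 25%/2.5 = 10%. Example at WBC 8,000: Day 1 is 4,000/µL and Day 4 is 480/µL (12%), which is 30 parasites per 500 and reads 30 × 8,000/200 = 1,200/µL (30%). This needs a Day 1 density from WBC/2 to just under 5 × WBC, or 5,000 to 50,000/µL at WBC 10,000. The Day 3 criterion can misfire at true ratios above 1/2.5 = 40%, but only for Day 1 densities below 1.25 × WBC (12,500/µL at WBC 10,000).
- *Same rule on all films, both days extended.* The factor cancels.
- *Extension on the pre-inclusion film only, as the heading literally says, with that film supplying the Day 1 count.* An extended Day 1 count is inflated and Day 4 is not. The ratio reads r/2.5, so 25% is reached only at r = 62.5%, and true ratios from 25% to just under 62.5% are missed.

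Under one common rule the third case cannot hide a Day 4 failure. If Day 1 was extended and Day 4 was not, then r exceeds 100% and still reads above 40%.

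**The case against.** The strongest reply is that the formula does not fix the denominator at 200. It names the number of leukocytes counted, with 200 in brackets. A microscopist who counted 500 and follows the label divides by 500 and gets the right density. That stands. A reader might infer that low densities in this trial *are* overstated, but neither document shows a site or the central laboratory dividing an extended count by 200. It does not remove the conflict: 200 is the only number in the formula, and the rule just before it requires 500 for these slides.

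A reader might also infer that the 25% rule will produce false early failures. The text does not establish this. The extension and the formula stand under the screening film, and the core-period bullets are silent. The ratio can therefore be raised, left alone or lowered (step 4). The footnote's reference to the latest available WBC suggests use beyond screening, but does not settle it.

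A third reply is that efficacy endpoints come from the central reading. That limits the reach, but not fully. The central denominator is not stated, nothing says that central reading corrects entry decisions, and rescue given after a local ETF call counts as failure in ACPR (SAP 2.7.2.1).

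Finally, recomputing every slide would presume an error that has not been shown. That stands, and the check proposed below is limited accordingly.

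**Conclusion.** The point holds as a conflict in the text with a definite size under one of its two readings. Applied as printed to an extended slide, the formula overstates density exactly 2.5-fold, independently of WBC. It would admit true densities of 200 to 499/µL in Cohort 1 and 40 to 99/µL in Cohort 2, and keep those patients in the per-protocol set under INCL04A/B. How many patients are affected, if any, cannot be told from the documents.

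The effect on the two density-based ETF criteria is possible but of uncertain direction. It would be wrong to read this as a threat to the main results. Artemether Cmax in the PK set does not use density. SAP 2.1.1 defines parasitaemia as any asexual count above zero, so late failure does not depend on the denominator. Nor does parasite clearance, which rests on the disappearance of asexual forms. The full analysis set needs only *P. falciparum* present at screening.

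**What to change.** - In the Protocol 8.3 formula, replace the bracketed 200 with *number of leukocytes actually counted (200 or 500)*.
- State that the same counting rule and formula apply to screening, core-period and central readings. This also closes the gap in the core-period text on which the ETF comparisons depend.
- Record the denominator with each slide, in the eCRF for local readings and in the data transfer for central readings.
- Before database lock, check whether any extended slide was divided by 200. If so, recompute those densities and re-derive INCL04A/B and the two density-based ETF criteria for those patients only.

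The cost is a short text correction, one data field and a limited check of raw counts where they were kept; the documents do not say that they were. Protocol 14.1 requires a written amendment with the usual approvals, so the text change is not free. It adds no patients, visits or blood draws.
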